## 8.2. Key Secondary Efficacy Analyses

The key secondary endpoint of Cumulative CS dose from baseline to Week 37, adjusted for time to study discontinuation will be calculated using the summation of the CS data as described in Section 6.1.9 and will be analyzed using an ANCOVA model with terms for treatment group and disease history. The estimated mean difference in cumulative CS usage (PRN1008 minus

placebo) and the associated 95% CI will be reported. Missing data for this endpoint is described in Section 6.1.5.2. The “time to study discontinuation” covariate is up to study discontinuation, first Rituximab administration if any, or the end of the blinded treatment period whichever happens first.

If outliers or skewed data is present, sensitivity analysis will be conducted on this secondary endpoint of average weekly CS usage over 36 weeks in which the data will be rank-transformed prior to analysis.

Cumulative CS dose from Week 37 to Week 61 will be analyzed similarly.

Cumulative duration of CR with CS dose  $\leq 10$ mg/day from Baseline to Week 37, will be based on a zero-inflated negative binomial model with terms for treatment group and disease history. The p-value and estimated treatment difference (parameter difference of PRN1008 minus placebo) from the negative binomial component will be reported, along with the 95% CI for the estimated parameter. The difference estimate will also be back-transformed (e.g. exponentiated) to demonstrate the relative difference in the number of pemphigus free days between treatment groups. Cumulative duration of CR with CS dose  $\leq 10$ mg/day from Baseline to Week 37 will also be summarized based on descriptive statistics.

A Kaplan Meier analysis will be used to estimate the median and other quartiles for Time (Days) to first CR with a dose of  $\leq 10$  mg/day, along with two-sided 95% confidence intervals. The number of events and censored observations will be presented as well as graphical representations of estimated survival curves. A hazard ratio for treatment comparisons will be presented, along with its 95% confidence interval, based on a Cox regression model with terms for treatment group and disease history. The endpoint will be evaluated based on a p-value from a log-rank test stratified by disease history for treatment group comparison. In addition, a landmark analysis will be done at Week 37 in the key secondary analysis and at Week 61 for the other secondary analysis.

All key secondary endpoints will be analyzed based on the subgroups presented in Section 6.1.3.2.

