### **2.3.2.2. Key Secondary Efficacy Endpoints**

The key secondary efficacy endpoints of this study include the following, ranked in order of importance:

1. Cumulative CS dose from Baseline to Week 37
2. Cumulative duration of CR with a CS dose  $\leq 10$  mg/day, from Baseline to Week 37
3. Time to first CR with a CS dose  $\leq 10$  mg/day CS, from Baseline to Week 37

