## 4. Statistical Analysis and Reporting

### 4.1. Introduction

Data processing, tabulation of descriptive statistics, calculation of inferential statistics, and graphical representations will be performed primarily using SAS (release 9.4 or higher). If the use of other software is warranted, the final statistical methodology report will detail what software was used for what purposes.

Continuous (quantitative) variable summaries will include the number of subjects ( $n$ ) with non-missing values, mean, standard deviation (SD), median, minimum, and maximum.

Categorical (qualitative) variable summaries will include the frequency and percentage of subjects who are in the particular category or each possible value.

Analyses will be presented by the treatment group assigned at randomization for the Blinded Treatment Period of the study and by double-blind treatment group and overall for the Open Label Phase and Long-Term Extension Phase of the study, unless stated otherwise.

The minimum and maximum will be reported with the same degree of precision (i.e., the same number of decimal places) as the observed data. Measures of location (mean and median) will be reported to 1 degree of precision more than the observed data and measures of spread (SD) will be reported to 2 degrees of precision more than the observed data.

Percentages will be presented to 1 decimal place, unless otherwise specified.

Unless otherwise indicated, all statistical tests will be conducted at the 0.05 significance level using 2-tailed tests, and  $P$  values will be reported. Corresponding 95% confidence intervals (CIs) will be presented for statistical tests.

Statistical testing will be performed at the 0.05 level using two-tailed tests.

To control for the overall type I error rate, hierarchical testing based on a fixed sequence procedure will be used. If statistical significance is declared for the primary analysis, formal hypothesis testing will be done for the key secondary endpoints in sequence until a non-significant result is reached. All other  $p$  values from key secondary and other secondary endpoints, after a non-significant  $p$  value is reached, will be considered nominal.

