##### **6.1.4. Multiple Comparisons**

The type I error rate of  $\alpha = 0.05$  will be maintained for the study by using sequential (hierarchical) testing for the primary and key secondary endpoints.

The testing will be done in the following order:

1. Primary endpoint based on PV patients in mITT population

2. Primary endpoint in mITT population (ie, PV+PF patients)
3. Key secondary endpoints based on PV patients in mITT population (in the order presented in Section 2.3.2.2)
4. Key secondary endpoints in mITT population (ie, PV+PF patients) (in the order presented in Section 2.3.2.2)

The study will be declared to be a positive study if the p-value for the primary endpoint based on PV patients in the mITT population is significant at two-sided  $\alpha = 0.05$  level. The test stops as soon as an endpoint is found not statistically significant at  $\alpha=0.05$  (2-sided). The nominal p-values for subsequent tests without adjustment will be provided in the summary tables for information purpose.

All other endpoints will be considered exploratory, and no adjustments will be made for multiple comparisons.

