**Table 6: Efficacy Endpoints and Analysis Methods**

	Endpoint	Analysis Method
Primary	Proportion of patients who are in CR from Week 29 to Week 37 with a CS dose of $\leq 10$ mg/day	Cochran-Mantel-Haenszel test stratified by disease history (newly diagnosed or relapsing).
Secondary Endpoints (in hierarchy)	Cumulative CS dose from Baseline to Week 37	Analysis of covariance, with CS dose duration (in days) during the blinded treatment period time to study discontinuation as the covariate, with terms for treatment group, and disease history.
	Cumulative duration of CR with CS dose $\leq 10$ mg/day from Baseline to Week 37 (days)	Zero-inflated negative binomial with terms for treatment group and disease history with an offset term based on the number of days on study during the Blinded Treatment Period
	Time (Days) to first CR with a dose of $\leq 10$ mg/day from Baseline to Week 37	Log rank test stratified by disease history
	Proportion of patients with at least one disease flare/relapse from initial control of disease activity (CDA) to Week 37	Cochran-Mantel-Haenszel test stratified by disease history
	Cumulative duration of CR with CS dose $\leq 10$ mg/day from Week 37 to Week 61 (days)	Zero-inflated negative binomial with terms for treatment group and disease history with an offset term based on the number of days on study during the Blinded and unblinded Treatment Period
	Cumulative duration of CR with CS dose = 0 mg/day from Week 37 to Week 61 (days)	Zero-inflated negative binomial with terms for treatment group and disease history with an offset term based on the number of days on study during the Blinded and unblinded Treatment Period

	Endpoint	Analysis Method
Secondary Endpoints (not in hierarchy, family-wise error rate not controlled)	The proportion of patients who are in CR from Week 29 to Week 37 with a CS dose of $\leq 5$ mg/day	Cochran-Mantel-Haenszel test stratified by disease history
	The proportion of patients who have PDAI score $< 3$ from Week 29 to Week 37 with CS $\leq 10$ mg/day	Cochran-Mantel-Haenszel test stratified by disease history
	Cumulative duration of CR with a CS dose of $\leq 10$ mg/day (days) from Baseline to Week 61	Zero-inflated negative binomial with terms for treatment group and disease history with an offset term based on the number of days on study during the Open-Label Extension Period

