### 8.3. Other Secondary Analyses

The following endpoints will be analyzed in a manner similar to that described for the primary endpoint in Section 8.1, with exception of the additional subgroup analyses described in Section 6.1.3.2:

- The proportion of patients who are in CR from Week 29 to Week 37 with a CS dose of  $\leq 5$  mg/day
- The proportion of patients who have a PDAI score  $< 3$  from Week 29 to Week 37 with CS  $\leq 10$  mg/day

Cumulative duration of CR with a CS dose  $\leq 10$  mg/day from Baseline to Week 61; cumulative duration of CR with a zero CS dose from Baseline to Week 61 and the cumulative duration of CR with a zero CS dose from Week 37 to Week 61 will be analyzed based on the same methods described for the cumulative duration of CR with CS dose  $\leq 10$ mg/day from Baseline to Week 37.

Change from baseline to Weeks 5, 13, 25, 37, and 61 in PDAI will be analyzed using restricted maximum likelihood (REML)-based mixed model for repeated measures (MMRM) with fixed effects for treatment, week, baseline PDAI and treatment by week interaction. For the analysis of the differences at Weeks 5, 13, 25, and 37, only all data up to Week 37 will be included in the model. For the analyses of the difference at 61 weeks, only data collected during the Open-Label Extension Period will be included in the model (from Week 39 onward). A contrast will be written within the MMRM model to get each Week-specific treatment difference (least squares treatment means, treatment difference estimates and 95% CIs). ABQOL and EQ-5D-5L overall VAS scores will be analyzed similarly.

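### Key secondary 2 (days in CR on ≤10 mg/day): the only p-value named comes from the negative binomial component, so a gain from more patients reaching CR goes untested within this endpoint and the reported ratio is mislabelled

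*SAP*

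**What the plan says.** Key secondary 2 is cumulative duration of CR with a CS dose of at most 10 mg/day, baseline to Week 37. It is second of three in the list that SAP 2.3.2.2 opens with "The key secondary efficacy endpoints of this study include the following, ranked in order of importance". SAP section 8 places the efficacy analyses in the mITT population.

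SAP 8.2 specifies a zero-inflated negative binomial model with treatment and disease history. Table 6 adds exposure, "with an offset term based on the number of days on study during the Blinded Treatment Period". The inferential output is then defined: "The p-value and estimated treatment difference (parameter difference of PRN1008 minus placebo) from the negative binomial component will be reported", with a 95% CI for that parameter. The estimate is exponentiated to "demonstrate the relative difference in the number of pemphigus free days between treatment groups". The only other output is descriptive. Table 6 and Protocol 9.3.5 give the model without naming a component or a test, and nowhere is it stated which part of the model the terms enter.

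For key secondary 3 (time to first CR), the same SAP section states a decision rule: "The endpoint will be evaluated based on a p-value from a log-rank test stratified by disease history for treatment group comparison". SAP 4.1 says "formal hypothesis testing will be done for the key secondary endpoints in sequence until a non-significant result is reached", and SAP 6.1.4 says "The test stops as soon as an endpoint is found not statistically significant at" the two-sided 0.05 level. The order is: primary in PV, primary in PV+PF, the three key secondaries in PV, then the three in PV+PF. SAP 8.3 says that further CR-duration endpoints "will be analyzed based on the same methods described for the cumulative duration of CR with CS dose" of at most 10 mg/day to Week 37.

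**The concern.** A zero-inflated model answers two questions: does a patient have any CR days (zero part), and if so how many (count part)? The endpoint combines both, counted over all mITT patients. SAP 8.2 takes its p-value, estimate and CI from the count part alone.

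Patients who never reach CR are absorbed almost entirely by the zero part. The count coefficient therefore in effect compares durations among remitters, a subset formed after randomisation. A drug that brings more patients into remission gets no credit for that within this endpoint. The exponentiated coefficient equals the between-group ratio of CR days only if equal shares of the two arms reach CR.

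The stakes are in the fixed sequence. If both primary tests pass and cumulative CS dose passes in PV, this test comes next. A non-significant result in PV makes four later tests nominal: time to first CR in PV, and all three key secondaries in PV+PF. The published ratio would also be read as something it is not.

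**Working it through.** **Plan figures.** The documents give no power, effect size or CR duration for this endpoint, so there is nothing to reproduce. The only planning rates visible are 15% vs 50% for the primary, in superseded text (Protocol Appendix 13, Version 5). They are used here only as one scenario.

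**Step 1: where the zeros go.** For a negative binomial, P(0) = (1 + dispersion × mean)^(−1/dispersion).
- Mean 57 days, dispersion 0.6: (1 + 34.2)^(−1.667) = 0.3%.
- Mean 30 days, dispersion 0.6: (1 + 18)^(−1.667) = 0.7%.

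The count part produces almost no zeros, so patients without CR land in the zero part.

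**Step 2: what the ratio measures.** Ratio of mean CR days = (ratio of shares reaching CR) × (ratio of mean duration among remitters). The count coefficient estimates the second factor only.
- 15% vs 50%, equal durations: (0.50/0.15) × 1 = 3.3; count part 1.
- 30% vs 60%, durations 20% longer on drug: 2.0 × 1.2 = 2.4; count part 1.2.
- Case 3d below, taking range midpoints (125.5 and 35 days) as means: placebo 0.15 × 125.5 + 0.25 × 35 = 27.6 days over all patients, or 27.6/0.40 = 68.9 among remitters. Drug 0.50 × 125.5 + 0.10 × 35 = 66.25, or 66.25/0.60 = 110.4. Overall ratio 2.4; remitter ratio 1.6.

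**Step 3: simulation.** There were 49 PV patients per arm ((120 − 22)/2, from the enrolment targets) and 2,000 trials per case. Treatment and history were in both parts, with offset log days on study and Wald tests. The overall-mean contrast was standardised over history by the delta method. Van Elteren was stratified by history. Sustained CR runs to day 253. Transient CR starts on days 57–197 and counts as primary non-response. The first three result columns give the percentage of trials significant in favour of drug.

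| Case (placebo vs drug) | Count part | Overall mean | Van Elteren | True ratio | Median exp(count coef.) |
|---|---|---|---|---|---|
| 1a: 15% vs 50% reach CR, 56–195 days | 4 | 93 | 96 | 3.3 | 1.00 |
| 1b: 30% vs 60%, 30–150 days | 3 | 74 | 82 | 2.0 | 1.00 |
| 2a: 30% vs 60%, CR 20% longer on drug | 30 | 92 | 91 | 2.4 | 1.21 |
| 2b: 30% vs 60%, CR 40% longer on drug | 72 | 98 | 95 | 2.8 | 1.40 |
| 3a: 15% vs 50% sustained, plus transient 15% vs 15%, 14–56 days | 31 | 94 | 97 | 2.8 | 1.31 |
| 3b: as 3a, transient 15% vs 10% | 44 | 94 | 93 | 2.8 | 1.39 |
| 3c: as 3a, transient 25% vs 10%, 28–84 days | 68 | 86 | 80 | 2.1 | 1.40 |
| 3d: as 3a, transient 25% vs 10% | 76 | 90 | 81 | 2.4 | 1.62 |

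Selected cases with 45 per arm, or with dropout 20% vs 15%, gave 3–6% for the count part in group 1 and 72% in case 3d; van Elteren gave 76–96%.

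**Step 4: effect on the sequence.** Among trials passing a proxy for the PV primary, the count part is non-significant in 95–96% (group 1), 27–67% (group 2) and 22–68% (group 3). In 94–95%, 26–66% and 11–64% of them, key secondary 3 in PV would be significant but becomes nominal. The PV+PF primary, cumulative CS dose and rituximab were not modelled.

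**Step 5: a second simulation** (60 per arm, 300 trials, full follow-up, days capped at 1–252) agrees.
- 15% vs 50% with mean 90 days in both arms: count part 6.0%, Wilcoxon 99.0%, exponentiated coefficient 1.03 vs overall ratio 3.31.
- 45% in both arms, 70 vs 110 days: 1.53 vs 1.50, so the label fits when the shares are equal.
- 30% vs 60%, 110 vs 65 days: coefficient 0.61, significant in 66% of trials with the estimate favouring placebo, while overall CR days are 1.23 times higher on drug.

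**The case against.** **The p-value is only to be reported; no decision role is stated.** True, and its role is inferred. But it is the only p-value named for an endpoint in the fixed sequence. If it does not decide, the confirmatory test is unspecified, which also needs correcting.

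**Treatment might enter the count part only.** The exponentiated coefficient would then formally be the model's overall mean ratio, so the label would fit that model. The model would, however, be misspecified, and the estimate still misses the gain: 1.03 against 3.31 at 15% vs 50%, with 6.0% rejection.

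**Reaching CR is tested elsewhere.** The primary and key secondary 3 do test it. Key secondary 3 comes after this endpoint, though, and neither estimates CR days. The SAP's own label compares treatment groups, not remitters, so a remitters-only target is not what it states.

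**Near-total power loss is an extreme case.** This stands. The protocol describes a fast-acting drug, and earlier sustained CR adds days among remitters, which the count part detects. In case 3d it reaches 76%, against 81% for van Elteren.

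**The Step 4 percentages condition on the PV primary alone.** Also true. If cumulative CS dose fails first, key secondary 3 is nominal whatever happens here, so these are not unconditional probabilities of blocking.

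**Conclusion.** The point holds and should be fixed. What rests on the text is certain: SAP 8.2 names a test of one component only, and attaches to its exponential a description that is correct only when equal shares reach CR. The size of the power loss is not certain, because the documents give no CR durations and the derivation of CR days is not visible in the public text. Over the assumed cases it runs from near total (3–4% against 74–96% for all-patient tests) to small (76% against 81–90%). The ratio is understated in all eight tabulated cases.

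No inflation of type I error is claimed, and the primary analysis is not affected. The study is still declared positive on the PV primary alone. The exposure is limited to this endpoint's result and the four tests behind it.

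**What to change.** In SAP 8.2 and Table 6, name one confirmatory test on all mITT patients, including those with zero CR days. The smallest change is the treatment contrast in overall mean CR days from the planned model. It keeps the days-on-study offset and states that treatment and disease history enter both parts. That statement matters: with an intercept-only zero part, this contrast favours drug in only 3–5% of trials in the two similar-duration cases (1,000 trials each). An alternative is a van Elteren test stratified by disease history, with a stated rule for days after dropout or rituximab.

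Report the overall mean ratio or difference as the estimate. Keep the two components as supportive output, labelled *odds of any CR* and *duration among remitters*, and delete the pemphigus-free-days reading of the count coefficient. Carry the change to the CR-duration endpoints in SAP 8.3. Protocol 9.3.5 defers detail to the SAP but should be aligned.

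The cost is wording and one program before unblinding, plus power if the drug only lengthens CR. With 40% reaching CR in both arms, and 30–150 days on placebo vs 45–195 on drug, the count part favours drug in 64%, the overall-mean contrast in 18% and van Elteren in 8%. The PV primary passes in only 8% of those trials, so the test would rarely be reached. Under a null case (30% sustained and 10% transient CR in both arms, dropout 20% vs 15%), two-sided rejection is 5.0%, 4.4% and 4.3% respectively.

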### 8.3. Other Secondary Analyses

The following endpoints will be analyzed in a manner similar to that described for the primary endpoint in Section 8.1, with exception of the additional subgroup analyses described in Section 6.1.3.2:

- The proportion of patients who are in CR from Week 29 to Week 37 with a CS dose of  $\leq 5$  mg/day
- The proportion of patients who have a PDAI score  $< 3$  from Week 29 to Week 37 with CS  $\leq 10$  mg/day

Cumulative duration of CR with a CS dose  $\leq 10$  mg/day from Baseline to Week 61; cumulative duration of CR with a zero CS dose from Baseline to Week 61 and the cumulative duration of CR with a zero CS dose from Week 37 to Week 61 will be analyzed based on the same methods described for the cumulative duration of CR with CS dose  $\leq 10$ mg/day from Baseline to Week 37.

Change from baseline to Weeks 5, 13, 25, 37, and 61 in PDAI will be analyzed using restricted maximum likelihood (REML)-based mixed model for repeated measures (MMRM) with fixed effects for treatment, week, baseline PDAI and treatment by week interaction. For the analysis of the differences at Weeks 5, 13, 25, and 37, only all data up to Week 37 will be included in the model. For the analyses of the difference at 61 weeks, only data collected during the Open-Label Extension Period will be included in the model (from Week 39 onward). A contrast will be written within the MMRM model to get each Week-specific treatment difference (least squares treatment means, treatment difference estimates and 95% CIs). ABQOL and EQ-5D-5L overall VAS scores will be analyzed similarly.

Descriptive summaries presenting the raw scores and change from baseline will be presented for ABQOL, PDAI, and EQ-5D-5L and EQ-5DVAS scores by treatment group at each study visit. Additionally, descriptive summaries for responses to the EQ-5D-5L dimensions of mobility, self-care, usual activities, pain/discomfort, and anxiety/depression will be displayed as frequency counts by category and treatment group for each study visit (Week 37, as well as Weeks 5, 13, 25 and 61). Results will be analyzed using a CMH test, stratified by disease history. The observed number and proportion of subjects reporting No Problems, as well as the resulting Mantel-Haenszel risk difference (PRN1008 – placebo), estimated SE, 95% CI and the associated p-value will be reported. Descriptive summaries will be presented separately for the blinded treatment, open label, and long term extension periods of the study.

The proportion of patients with 3 or more lesions within 1 month or extension of established lesions that do not heal spontaneously within 1 week from Baseline to Week 37 will be analyzed using the same methodology as the primary endpoint as described in Section 8.1. The total number of disease flares/relapses from initial CDA to Week 37 will be analyzed based on the same methodology described for the cumulative duration of CR with CS dose  $\leq$  10mg/day from Baseline to Week 37 in Section 8.2.

A Kaplan Meier analysis will be used to estimate the median and other quartiles for Time to first flare/relapse from initial CDA to Week 37, along with two-sided 95% confidence intervals. The number of events and censored observations will be presented as well as graphical representations of estimated survival curves. A hazard ratio for treatment comparisons will be presented, along with its 95% confidence interval, based on a Cox regression model with terms for treatment group and disease history. The endpoint will be evaluated based on a p-value from a log-rank test stratified by disease history for treatment group comparison.

Descriptive statistics including number, mean, SD, SE, median, minimum, and maximum will be provided by treatment group and by visit for domain-specific GTI scores, composite GTI total score, CWS and AIS. For CWS and AIS at Week 37, analysis of covariance model with treatment, disease history as fixed effects, and baseline GTI score, baseline CS dose as covariates, will be used to test the difference of the least-square means (LS means) between the treatment groups. Difference in LS means and the corresponding 95% CI along with the p-value will be provided.

Proportion of patients with at least one disease flare/relapse from initial control of disease activity (CDA) to Week 37 will be analyzed using the same methodology as the primary endpoint as described in Section 8.1.

Cumulative duration of CR with a CS dose  $\leq 10$  mg/day from Week 37 to Week 61, and cumulative duration of CR with a CS dose = 0 mg/day from Week 37 to Week 61 will be analyzed similarly to cumulative duration of CR with CS dose  $\leq 10$ mg/day from Baseline to Week 37.

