### **Other secondary:**

The other secondary endpoints will be primarily analyzed descriptively.

The change from baseline in GTI, ABQOL, PDAI, and EQ-5D-5L overall visual analogue scale (VAS) scores to each visit will also be analyzed using restricted maximum likelihood (REML)-based mixed models for repeated measures (MMRM) with fixed effects for treatment, week, Screening score, and the treatment-by-week interaction.

The proportion of patients who are in CR from Week 29 to Week 37 with a CS dose of  $\leq 5$  mg/day of CS at any time will be compared using the same method as the primary endpoint.

The difference in the proportion of patients with 3 or more lesions within 1 month that do not heal spontaneously within 1 week, or with extension of established lesions, from Baseline to Week 37, will be tested in the same manner as the primary endpoint.

Proportion of patients with at least one disease relapse/flare from initial CDA to Week 37 will be tested in the same manner as the primary endpoint.

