### 3.5. Method of Assigning Subjects to Treatment Groups

Patients who meet study criteria will be randomly assigned to placebo or PRN1008 in an approximately 1:1 allocation ratio. The randomization scheduled will be computer generated using a permuted block algorithm stratified by PV/PF disease type and by relapsing/newly diagnosed disease history (newly diagnosed defined as within 6 months of Screening).

The randomization schedule will be prepared by Premier Research before the start of the study. No one involved in the study performance will have access to the randomization schedule before the official unblinding of treatment assignment. No subject will be randomized into this study more than once.

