## **6. General Issues for Statistical Analysis**

### **6.1. Statistical Definitions and Algorithms**

#### **6.1.1. Baseline Definitions**

Baseline values will be the last observation recorded prior to first dose of randomized treatment. Baseline value derivations will include evaluations specified to have been collected Pre-Dose on Day 1 as specified in study schedule. For patients from the ITT Population who are randomized but not treated, baseline will be based on their randomization date.

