#### **6.1.3. Adjustments for Covariates and Subgroup Analyses**

##### **6.1.3.1. Covariates**

Disease history (newly diagnosed or relapsing) will be taken into account by including as a stratification variable or covariate in all of the analyses except for the Chi-Square analyses. Due to the small number of PF subjects expected to be enrolled in the study, the randomization strata of disease type will not be included as a covariate in any of the analyses.

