	Cumulative duration of CR with a CS dose = 0 mg/day (days) from Baseline to Week 61	Zero-inflated negative binomial with terms for treatment group and disease history with an offset term based on the number of days on study during the Open-Label Extension Period
	GTI scores at Week 37	Analysis of covariance, with treatment, disease history as fixed effects, and baseline GTI score, baseline CS dose as covariates
	Change from Baseline in PDAI Score at Weeks 5, 13, 25, 37, and 61	MMRM with terms for treatment, week, baseline score, disease history, and treatment by week interaction
	Change from Baseline in ABQOL Score at Weeks 5, 13, 25, 37, and 61	MMRM with terms for treatment, week, baseline score, disease history, and treatment by week interaction
	Proportion of patients with ABQOL Score of zero at Weeks 5, 13, 25, 37, and 61	Cochran-Mantel-Haenszel test stratified by disease history at each visit
	Change from Baseline in EQ-5D-5L visual analog scale [VAS] results and individual dimension score categories at Weeks 5, 13, 25, 37 and 61	Continuous outcomes: MMRM with terms for treatment, week, baseline score, disease history, and treatment by week interaction. Categorical outcomes: Cochran-Mantel-Haenszel test stratified by disease history

	Endpoint	Analysis Method
	Time to first flare/relapse from initial CDA to Week 37	Log rank test stratified by disease history
	Time to first CR with a CS dose $\leq$ 10mg/day, from Baseline to Week 61	Log rank test stratified by disease history
	Proportion of patients with 3 or more lesions within 1 month or extension of established lesions that do not heal spontaneously within 1 week from Baseline to Week 37	Cochran-Mantel-Haenszel test stratified by disease history
	Total number of disease flares/relapses from initial CDA to Week 37	Zero-inflated negative binomial with terms for treatment group and disease history with an offset term based on the number of days on Post initial CDA

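### SAP 8.3 leaves disease history out of the MMRM that Table 6 and SAP 6.1.3.1 say must contain it, and no rule in the SAP says which list governs

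*SAP*

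**What the plan says.** Four places bear on the MMRM for the continuous other secondary endpoints.

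- SAP Section 8.3 gives the PDAI model as "fixed effects for treatment, week, baseline PDAI and treatment by week interaction", and has ABQOL and the EQ-5D VAS analysed in the same way.
- SAP Table 6, for PDAI, ABQOL and the continuous EQ-5D outcome, gives "MMRM with terms for treatment, week, baseline score, disease history, and treatment by week interaction".
- SAP Section 6.1.3.1 sets the general rule that disease history enters as a "stratification variable or covariate in all of the analyses except for the Chi-Square analyses". It treats the other stratum differently: "the randomization strata of disease type will not be included as a covariate in any of the analyses".
- Protocol Section 9.3.6, under other secondary endpoints, gives "fixed effects for treatment, week, Screening score, and the treatment-by-week interaction".

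SAP Section 3.5 describes randomisation by a "permuted block algorithm stratified by PV/PF disease type and by relapsing/newly diagnosed disease history". The introduction to SAP Section 8 presents Table 6 as the summary and says the sections after it give more detail. It does not say what happens if the two disagree.

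**The concern.** The SAP contains two different fixed-effect lists for the same endpoints, and they differ by a randomisation stratum. Someone programming from Section 8.3 would fit one model, and someone programming from Table 6 another. Both could point to the SAP. A pre-specified plan should not leave that choice open at unblinding.

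There is also a possible cost in precision. When randomisation is balanced within a stratum that predicts outcome, the treatment estimate is already protected from imbalance on it. A model that ignores the stratum nevertheless puts the between-stratum variation into the residual. The reported standard error is then larger than it should be.

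**Working it through.** **1. The lists side by side**

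| Place | Score adjusted for | Disease history | Treatment, week, treatment-by-week |
|---|---|---|---|
| SAP 8.3 | baseline | absent | yes |
| SAP Table 6 | baseline | present | yes |
| SAP 6.1.3.1 (general rule) | not addressed | required, except in Chi-Square analyses | not addressed |
| Protocol 9.3.6 | Screening | absent | yes |

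An MMRM is not a Chi-Square analysis. The exception fits the unstratified Pearson fallback that SAP Section 8 provides for sparse strata. So Section 8.3 departs from both Table 6 and the general rule.

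**2. Is the omission just shorthand?** Where Section 8 wants disease history in a model, it usually names it: the ANCOVA, negative binomial and Cox models in 8.2, and the Cox model and GTI ANCOVA in 8.3. Against that background, the MMRM sentence reads as a complete list.

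**3. Size of the precision effect.** The documents state no SD, effect size or power for any MMRM endpoint, so there is no figure to reproduce. The range below rests on assumptions.

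Inputs:
- N = 120, allocated 1:1 (Protocol synopsis).
- Two-sided alpha 0.05 (SAP 4.1).
- p, the share newly diagnosed: assumed 0.3 to 0.5.
- d, the effect of disease history on the change score in residual SDs, after adjusting for baseline score: assumed 0 to 1.

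Formulas:
- SE inflation when the term is omitted = sqrt(1 + p(1−p)d²).
- Power of an analysis that would have 80% with the term = Φ((1.960 + 0.842)/inflation − 1.960).

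Worked example, p = 0.4 and d = 0.5: p(1−p)d² = 0.24 × 0.25 = 0.06; inflation = sqrt(1.06) = 1.030; power = Φ(2.802/1.030 − 1.960) = Φ(0.76), about 78%.

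| d | SE inflation, p = 0.3 to 0.5 | 80% power becomes |
|---|---|---|
| 0 | none | 80% |
| 0.25 | 0.7 to 0.8% | about 79% |
| 0.5 | 2.6 to 3.1% | about 78% |
| 0.75 | 5.7 to 6.8% | about 75% |
| 1.0 | 10.0 to 11.8% | 71 to 72% |

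**4. Check by simulation.** N = 120, arms exactly balanced within strata, p = 0.4, 6000 runs. A single-visit ANCOVA on complete data, with baseline score, stands in for one week's MMRM contrast.

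| d | SE ratio, omitted / included | Type I error, omitted vs included | Power, omitted vs included |
|---|---|---|---|
| 0 | 1.00 | 5.1% vs 5.1% | 79.1% vs 79.1% |
| 0.5 | 1.03 | 3.9% vs 4.4% | 77.4% vs 78.9% |
| 1.0 | 1.11 | 3.1% vs 4.7% | 73.2% vs 79.8% |

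The Monte Carlo standard error on a 5% rate is sqrt(0.05 × 0.95/6000) = 0.0028, about 0.3 percentage points. The simulated ratios agree with the formula, and omission makes the test conservative.

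**The case against.** The best defence is that the SAP, read as a whole, already points to one model. Section 6.1.3.1 is a general rule and Table 6 agrees with it. Section 8.3 never says that disease history is excluded, whereas the SAP says so openly when it drops the disease-type stratum. The body text is also incomplete elsewhere: Section 8.2 does not repeat the offset that Table 6 gives for the cumulative-CR model. This has force, and including disease history is the better reading. It does not remove the conflict, because the SAP describes the later sections as the more detailed ones and gives no order of precedence.

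Several stronger readings are tempting, and the documents do not support them.

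- A reader might infer that the choice between Screening and baseline score is also open. It is not. The protocol synopsis makes the SAP the final authority on statistical analyses, both SAP lists use baseline, and SAP 6.1.1 defines it: "Baseline values will be the last observation recorded prior to first dose of randomized treatment".
- A reader might infer that disease history must be prognostic because the PDAI entry threshold (15 against 9) and the minimum starting corticosteroid dose differ by history. The threshold links history to baseline PDAI, which is already in the model. What matters is the effect left after that adjustment, and the documents give none.
- A reader might infer bias or inflated type I error. With randomisation stratified on disease history, the effect runs the other way.
- A reader might take the rule in 6.1.3.1 to cover both strata. It covers disease history only; disease type is left out on purpose.

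**Conclusion.** The contradiction within the SAP is real and does not depend on any calculation: Section 8.3 omits a term that Table 6 lists and Section 6.1.3.1 requires.

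Its consequence is small and of uncertain size. The loss of precision may be zero. It is about 3% of the standard error for a moderate residual effect (0.5 SD) and reaches about 12% at 1 SD. These figures rest on an assumed stratum mix and prognostic effect, on balance within strata, and on complete data; dropout was not simulated. Part of any disease-history effect may already be carried by the baseline score.

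The endpoints concerned are other secondary endpoints. SAP 6.1.4 treats them as exploratory and Table 6 places them outside the hierarchy, so neither the primary or key secondary tests nor familywise error control is touched. This is a worthwhile clarification, not a threat to the trial's conclusions.

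**What to change.** In SAP Section 8.3, state the MMRM fixed effects as treatment, week, baseline score, disease history and treatment-by-week, for PDAI and likewise for ABQOL and the EQ-5D VAS. That matches Table 6 and Section 6.1.3.1.

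The cost is one phrase in the SAP and one model degree of freedom. Disease history is already recorded for stratification, so no new data are needed. No protocol amendment is needed. The move from Screening score to baseline score can be recorded in SAP Section 10, which currently lists no changes from the planned analysis.
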